a) **Experimental Design:** The proposed study is a randomized trial evaluating the impact of a dietary and physical activity guidelines intervention vs. usual care on adherence to breast cancer treatments, body composition, and changes in biomarkers in 172 women newly diagnosed with breast cancer who will receive neoadjuvant or adjuvant chemotherapy as part of their treatment. The intervention will be conducted in person in the breast clinic at Smilow Cancer Hospital/Smilow Care Center and/or via telephone/video over one-year. When possible, assessments (4 in total) will be completed at a study baseline clinic visit (after diagnosis for women receiving neoadjuvant chemotherapy and after breast surgery for women receiving adjuvant chemotherapy, but prior to the second chemotherapy infusion) and post chemotherapy, at 1- and 2-yrs post-diagnosis. If not possible for a patient to travel to New Haven for the in-person study assessments, the patient will complete online or/and hard copy study questionnaires. These may be administered by phone. The assessments conducted at the in-person visit are optional at all timepoints. The assessments include: physical exam (height, weight, waist and hip circumference), DXA scan, blood and urine collection, grip strength and carotenoid assessment. Following publication of the initial primary results the manuscript will be mailed to all study participants. Participants who consented to be recontacted will be asked if they are willing to participate in a 5-year follow. Five-year follow up will include assessment of dietary intake, physical activity, and quality of life, similar to these 1- and 2-year assessments. Data regarding breast cancer recurrence, mortality and medical usage will be abstracted from the EMR.

Study Population: We will enroll 172 women over 2.5 years (~ 8-9 women/month). Women will be enrolled prior to their the second neoadjuvant or adjuvant chemotherapy session. Given treatments are often of a longer duration for stage IV (which includes recurrent breast cancer) breast cancer, women with stage IV will not be eligible. Patients with recurrent cancer, independent of whether they have received chemotherapy at the time of initial diagnosis, or the time that has elapsed since the initial diagnosis, are eligible. The treatment of the recurrent cancer must be intended to be curative.

Table 1. Eligibility Criteria

Inclusion Criteria:

- Diagnosed with Stage I-III breast cancer

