In July 2020, all women who are or who have been (if they agreed to future contact as indicated on the study consent form) participants in LEANer will be invited via email to complete an online or hard copy survey regarding the effect of the coronavirus epidemic on their cancer care, and their mental health, diet and physical activity. A link to the survey, which will be hosted on the Qualtrics platform, will be included in the email invitation with instructions on how to get the hard copy questionnaire if desired. The survey will take approximately 10-15 minutes to complete. A study staff member will follow up by email, text message or phone to confirm receipt of the invitation to complete the survey and answer any questions.

Newsletter: A newsletter will be mailed to all participants at 6-monthly intervals while enrolled in the study informing them of the progress of the study and providing relevant information with regard to breast cancer survivorship issues.

All assessments denoted * above are conducted at the in-person visits and are optional.

d) Randomization: Participants will be randomized into one of 2 study arms using a random permuted block design of varying block size in a 1:1 ratio (N=125 to intervention, 125 to usual care). To ensure participants with similar characteristics are equivalently assigned to the 2 groups, we will stratify on the following factors that may be associated with some of the study endpoints:

- i) chemotherapy regimen (≤ 4 cycles vs. >4 cycles)
- ii) hormone receptor status (ER/PR+ or not)
- iii) HER2 status (HER2+ve or not)

Resulting in six strata.:

- a) HR/PR+ve, HER2-ve, ≤ 4 cycles
- b) HR/PR+ve, HER2-ve, >4 cycles
- c) HR/PR-ve, HER2-ve, ≤ 4 cycles
- d) HR/PR-ve, HER2-ve, >4 cycles
- e) HR/PR+ve, HER2+ve, >4 cycles
- f) HR/PR-ve, HER2+ve, >4 cycles

The following study personnel will be masked to participant study arm: clinic medical staff performing the DXA scan and laboratory analysis.

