Participants who report that they have discontinued taking tamoxifen or AI will also be classified as nonadherent to endocrine therapy. For patients who may be lost to follow-up, we will obtain prescription refill data as an endpoint of adherence to endocrine therapy. For the endocrine

therapy aim, we will compare the crude adherence rates using simple logistic regression. Multivariate logistic regression will serve as supportive analyses including covariate adjustments – which are similar to the primary analysis above.

The secondary aims will be performed using Mixed Model Repeated Measures analysis incorporating Analysis of Covariance, where each woman's changes in outcome (follow-up measure – baseline) will be modeled as a function of treatment and time with a covariate included for the baseline value. Prior to fitting models, we will perform exploratory data analyses focusing on the distributions of biological markers by time and intervention group, assessing the appropriateness of log-transformation.

All hypotheses will be tested according to the intention-to-treat philosophy in which all randomized participants will be grouped according to their intervention assignment at randomization, regardless of compliance or adherence to the study. Statistical significance will be defined as $p < 0.05$, 2-sided. Since we have multiple outcomes, we will consider using a Bonferroni correction.

Age, menopausal status, race/ethnicity, BMI at diagnosis, disease stage, type of surgery, type of chemotherapy, radiation therapy, hormone receptor status, endocrine therapy, reconstructive surgery, type 2 diabetes, and smoking status will be examined as covariates. We will explore effect modification by menopausal status at diagnosis, hormone receptor status, and endocrine therapy.

We will further explore intervention effects on study endpoints by stratifying by adherence to diet and physical activity guidelines with a four-level category (e.g., met diet recommendations, met physical activity, met both diet and physical activity recommendations, or met neither recommendation). This analysis will allow us to better understand the role of diet vs. exercise on study endpoints.

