Although we do not anticipate an appreciable number of subjects lost-to-follow-up because of our plan of following patients during their medical oncology visits, the impact of missing data will be evaluated in the analysis. Bivariate logistic regression will be used to identify baseline variables associated with missingness. The primary analysis assumes missing data are missing at random (MAR). Under the MAR missing data mechanism, the probability of loss-to-follow-up depends only on the observed data. Non-random or informative loss-to-follow-up occurs when the missing data are dependent on the unobserved missing outcome values, latent and/or instrumental variables. Sensitivity analyses using methods for NMAR data will be considered.

Power and Sample Size Considerations: The sample size estimate was performed using PASS 12 (©2013 NCSS, LLC, Kayesville, UT). The original calculation was based on chemotherapy completion rates reported in the COMPAS study (Ziller etc, BMC Cancer, 2013). By assuming similar completion rate in our control arm, we estimated a sample size of 250 subjects would be needed. Sample size reevaluation was conducted using the aggregated data of first 51 LEANer participants who completed chemotherapy. The pooled standard deviation of RDI is 0.10. We re-estimated that a sample size of 86 subjects per arm (172 total) will achieve 90% power to detect a 0.05 (or 5%) difference in RDI between two arms at significance level of 0.05. For endocrine therapy adherence, the COMPAS study reported 48% of patients in the control group were adhering to AI therapy at 12 months.¹⁸ We assume approximately 50% of patients randomized to usual care in our study will be adhering to endocrine therapy at one-year post-initiation of use. Group sample sizes of 76 patients per group (or $N = 152$) provides 90% power to detect an absolute difference of 25% in the intervention group (50% vs. 75%, adherence in control and intervention groups, respectively) at a two-sided 0.05 significance level. We anticipate ~70% of participants (i.e., 70% of 172 = 120) will be prescribed endocrine therapy; thus an $N = 120$ will also allow for sufficient statistical power.

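### The randomization section still states 125 women per arm (250), although re-estimation replaced this with 86 per arm (172)

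*Combined protocol and SAP*

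**What the plan says.** Section I, 3(d) Randomization describes permuted blocks of varying size within six strata, with women allocated "in a 1:1 ratio (N=125 to intervention, 125 to usual care". Nothing there marks these arm sizes as historical.

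Section I, 12, Power and Sample Size Considerations, gives the history. On the initial assumptions, "we estimated a sample size of 250 subjects would be needed". A re-evaluation on aggregated data from the first 51 participants to complete chemotherapy then led to the current figure: "a sample size of 86 subjects per arm (172 total) will achieve 90% power to detect a 0.05 (or 5%) difference in RDI".

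The total of 172 also appears in Section I, 1 (Statement of Purpose), in 3(a) (Experimental Design and Study Population), in Section I, 5 (Subject Population) and in Section III, 1 (Targeted Enrollment, all sites). The closing paragraph of the power section uses 86 as the size of the intervention arm.

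On accrual, 3(a) says: "We will enroll 172 women over 2.5 years (~ 8-9 women/month".

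**The concern.** The section that defines allocation is where a reader looks for the planned number randomized, and it gives a size that the rest of the plan has replaced. A reduction made while the trial was running should be traceable throughout the protocol, because planned and actual enrolment will be compared later. One leftover figure also raises the question of whether others were missed. The accrual pace and the drop-out power statement both sit badly with 172, so they need the same check.

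**Working it through.** **1. The two sizes.** 3(d): 125 + 125 = 250. Power section: 86 + 86 = 172. Difference 250 − 172 = 78; 78/172 = 45% above the current target, or 78/250 = a 31% reduction.

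**2. Reproducing 86 per arm.** Inputs from Section I, 12: difference 0.05; "The pooled standard deviation of RDI is 0.10"; power 90%; "between two arms at significance level of 0.05"; and "Statistical significance will be defined as $p < 0.05$, 2-sided".

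- Normal approximation: n = 2 × (1.960 + 1.282)² × (0.10/0.05)² = 84.1, rounded up to 85 per arm.
- Two-sample t test: n = 85.03, rounded up to 86 per arm. This is the plan's figure.
- t-test power is 90.3% at 86 per arm. At 125 per arm it would be 97.6%, a figure the plan does not claim.

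The 172 is thus supported by the plan's own inputs. It contains no allowance for drop-out.

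**3. Accrual in 3(a).** 2.5 years is 30 months.

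- 8 × 30 = 240 and 9 × 30 = 270, so the stated pace and duration give 240-270 women, not 172.
- 172/30 = 5.7 a month if the duration holds.
- 172/9 = 19.1 and 172/8 = 21.5, so about 19 to 21.5 months if the pace holds.
- For comparison, 250/30 = 8.3 a month, inside the stated range.

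**4. Drop-out power statement.** The end of the power section states 81% power for 18% vs 34% dose adjustment, with 10% of 86 intervention women dropping out to usual care. Two-sided pooled z test, with p̄ the mean of the two rates:

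power = Φ{ [|p₁ − p₂| − 1.96 √(2p̄(1 − p̄)/n)] / √([p₁(1 − p₁) + p₂(1 − p₂)]/n) }

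- Rates as stated, n = 86, p̄ = 0.26: (0.160 − 1.96 × 0.0669)/0.0658 = 0.44, power **67.0%**. This also covers the reading that 18% already includes the drop-out.
- Effect diluted by drop-out: 0.9 × 18% + 0.1 × 34% = 19.6%. With n = 86, p̄ = 0.268: (0.144 − 1.96 × 0.0675)/0.0666 = 0.17, power **56.9%**.
- Rates as stated, n = 125: 82.6%. Diluted, n = 125: 73.2%.
- The stated rates need 120 per arm for 81% power.

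**5. Insulin.** The plan gives a difference of 3.0, SD 8.0 and 112 per group (224 total), without stating the power. At 80% power (my assumption): 2 × (1.960 + 0.842)² × (8/3)² = 111.6, rounded up to 112, which matches. The 224 exceeds 172. At 86 per arm the power is 69.1% by the same normal approximation.

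**The case against.** The strongest reply is that this is one stale parenthesis with no effect on the trial. Most of that stands.

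- A reader might infer that it is unclear which size governs. The documents do not support this: the power section says outright that 172 replaced 250, and every other enrolment statement agrees.
- A reader might infer that the randomization lists are affected. The 1:1 ratio, the permuted blocks and the six strata do not depend on the total.
- A reader might infer that the power statements rest on 125 per arm. None cites 3(d). RDI uses 86 per arm, endocrine adherence uses 70% of 172, and the drop-out statement uses 86.
- A reader might look for an enrolment stopping rule tied to 250. The documents set none beyond the target of 172.

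It is also fair to say that the 81% is a separate error, which editing 3(d) will not repair. Nor is its origin in 125 per arm shown: that size gives 82.6% with the stated rates and 73.2% with dilution, neither of which is 81%. Likewise, the accrual sentence shows a mismatch but not whether the pace or the duration is out of date.

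What remains is that a current section states a wrong sample size, and that two neighbouring figures do not fit the size that replaced it.

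**Conclusion.** The point holds as a correction to the text. The 125 per arm in 3(d) is superseded, and 86 per arm is the current and reproducible figure. The randomization method is unaffected, and the planned RDI power of about 90% stands, given an SD of 0.10, a difference of 0.05 and no loss of participants.

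The accrual sentence is inconsistent with 172 by 68 to 98 women (240 − 172 and 270 − 172). The 81% power figure is too high by about 14 percentage points with the rates as stated, or about 24 with the diluted effect, assuming a two-sided pooled z test at 0.05 without adjustment for strata. Both are separate from the error in 3(d) but belong in the same revision.

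The documents give a target and not the number enrolled, so nothing here says what size the trial reached.

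**What to change.** 1. In Section I, 3(d), replace 125 per arm with 86 per arm (172 total).
2. In Section I, 3(a), reconcile pace and duration: either about 5.7 women a month over 2.5 years, or 8-9 a month over about 19 to 21.5 months. The study team must say which applies.
3. In Section I, 12, recheck the secondary power figures at 172. Restate the 81% (about 67% with the rates as stated, about 57% with dilution) and say whether the 18% already includes drop-out. For insulin, give the power available at 86 per arm instead of a requirement of 224.

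Items 1 and 2 are text edits. Item 3 is a short recalculation. None changes allocation, data collection or the RDI analysis.

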*Skin carotenoid assessment: Reflectance Spectrometry (RS) is a quick novel noninvasive method of assessing skin carotenoids(88). Skin carotenoids measures will be conducted at the baseline, post-chemotherapy, 1-year and 2 year visits. The patient will apply gentle pressure on their thumb against the RS lens for less than one minute. Each patient's thumb will be scanned three times. RS values will be recorded on the laptop connected to the instrument. The RS methodology uses a broadband white light to measure skin carotenoids and other chromophores like melanin and hemoglobin directly through their respective absorptions. The reflected light is directed to a spectrograph coupled with a room-temperature detector array. The data processing algorithm corrects for the potentially confounding effects of melanin and tissue scattering (88). (Yale in-person visit only)

Side-effects and toxicity assessment: Women will complete the Patient-Reported Outcomes Version of the Common Terminology Criteria for Adverse Events (PRO-CTCAE™) at the BL and post-chemotherapy visits (https://healthcaresdelivery.cancer.gov/pro-ctcae/terms_of_use.html).

Lymphedema: Women will be screened for lymphedema the 1-year 2-year and 5-year follow ups by asking the following question ‘Since your cancer treatment, have you had any swelling on the same side as your treatment that has not gone away?’ If the response is ‘Yes’ then she will be asked about diagnosis of lymphedema and will complete the Norman Lymphedema Questionnaire. If lymphedema is reported any woman randomized to intervention, she will be instructed to wear a compression sleeve on the affected arm while strength training, and the upper body strength training will follow the model developed by Schmitz et al, in order to avoid lymphedema exacerbations. (89) These exercise protocols have been used by us before and are consistent with recommendations from the American College of Sports Medicine for cancer survivors.(89)

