Usual Care Group: Both our usual care group and intervention group will be provided with standardized breast cancer follow up care and materials regarding treatment (i.e., chemotherapy and endocrine therapy when relevant). Current chemotherapy regimens vary from 3 months to 5 months. About one-third of patients will receive four cycles of chemotherapy every 3 weeks, a total duration of ~3 months. About two-thirds of patients will receive four cycles of chemotherapy every 2 weeks followed by 12 weekly cycles of chemotherapy, a total duration of ~ 5 months. Each patient sees her medical oncologist at each chemotherapy session, and also at one- and two-months post-chemotherapy, and then every 3-6 months thereafter up to two years. Patients are seen semi-annually or annually; those on endocrine therapy are monitored by their oncologist semi-annually. Holiday cards will be mailed to all women while in study.

Lastly, we will also give women randomized to usual care a lifestyle intervention book and log book for breast cancer survivors and access to the associated online videos (approved for HIC protocol 1410014716).. Women will also be offered a counseling session with a registered study dietician at the end of the study.

Dietary and Physical Activity Guidelines Intervention Group:

When and Where: Patients receiving chemotherapy see their medical oncologist at least monthly during chemotherapy and then monthly or bi-monthly, ultimately tapering to semi-annually for several years. Thus, we have designed our intervention to be implemented in the breast clinic when the patient is seeing her medical oncologist. All intervention sessions can be completed by phone or video if this is the preference of the subject. Our LEAN study compared in-person lifestyle counseling to telephone-counseling, and found similar effectiveness on changes in diet and physical activity. For the proposed study, we have adapted our LEAN intervention to include a total of 16 x 30-min sessions over 12 months (3 times in the first month, then 2 times each month for months 2 through 5, and then 5 times over the next 6 months) timed with their oncology visit or via telephone or video (doxy.me) if preferred.

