Content of LEAN Counseling Sessions: Our dietary intervention is to counsel women on eating the recommended diet for cancer prevention and control, which focuses on diet quality and nutrient density, which are essential, especially when and if appetite is changed or diminished from treatment. The intervention is based on the LEAN protocol, which was developed by Drs. [name], [name] and [name]. All counseling sessions will be conducted by a registered dietitian. The intervention represents a core curriculum, using motivational counseling to address behavior strategies such as self-monitoring, goal setting, stimulus control, problem solving, and relapse prevention training. The intervention sessions are based on constructs of social-cognitive theory. The nutrition counseling promotes a predominantly plant-based diet, with extensive education on skill building to track portion sizes, fat grams, reduce simple sugars (including sugar sweetened beverages), limit consumption of salty foods and increase dietary fiber intake, resulting in an increased nutrient-dense eating pattern (see Table 3). Maintenance of a healthy BMI is also one of the recommended DHHS, ACS and WCRF/AICR lifestyle guidelines and associated with lower breast cancer mortality. Thus, our LEAN intervention, focusing on portion control and primarily a plant-based diet, will likely lead to better weight management. All topics are accompanied by a homework assignment. Of these, recording daily food intake and physical activity are the most important. Reported portion sizes, grams of fat, added sugars and fiber from the food journal will be compared with individualized goals at each counseling session. Women will also receive our 16-chapter manual adapted from the LEAN manual and a set of adapted recipes. The five new sessions that will be offered

**Table 3. Lifestyle Guidelines
Physical Activity Guidelines**

1. 150+ min/week of moderate to vigorous intensity physical activity or 75 min/week of vigorous-intensity physical activity
2. Twice-weekly strength training
3. Reduce sedentary time

Dietary Guidelines

4. Eat a combination of 5+ fruits and/or vegetables servings/day
5. Reduce simple sugars
6. Limit consumption of processed and red meats to \leq 18 ounces/week
7. Limit alcohol consumption to 1drink/day or 8 drinks/week

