6. **Subject classification:** Check off all classifications of subjects that will be specifically recruited for enrollment in the research project. Will subjects who may require additional safeguards or other considerations be enrolled in the study? If so, identify the population of subjects requiring special safeguards and provide a justification for their involvement.

Children

Healthy

Fetal material, placenta, or dead fetus

- Non-English Speaking Prisoners Economically disadvantaged persons
 Decisionally Impaired Employees Pregnant women and/or fetuses
 Yale Students Females of childbearing potential

NOTE: Is this research proposal designed to enroll children who are wards of the state as potential subjects? **Yes** **No**

7. Inclusion/Exclusion Criteria: What are the criteria used to determine subject inclusion or exclusion?

Inclusion Criteria:

- Diagnosed with Stage I-III breast cancer
- Will receive neoadjuvant or adjuvant chemotherapy as part of breast cancer treatment
- Physically able to walk
- Able to complete forms, understand instructions and read intervention book in English
- Agrees to be randomly assigned to either intervention or usual care group
- Aged 18 or over

Exclusion Criteria:

- Women who have had their second chemotherapy infusion
- Women already practicing dietary or physical activity guidelines
- Are pregnant or intending to become pregnant in the next year
- Recent (past year) stroke/myocardial infarction or congestive heart failure
- Presence of dementia or major psychiatric disease
- Women who are malnourished (PG-SGA assessment)
- Participating in a meal replacement weight loss program
- Non English speaking

8. How will **eligibility be determined, and by whom?**

Study eligibility will be determined by study personnel in concert with Drs. [name] and [name].

9. Risks: Describe the reasonably foreseeable risks, including risks to subject privacy, discomforts, or inconveniences associated with subjects participating in the research.

Assessment of the risk associated with participating in the study can be categorized as minimal. The nutritionist/counselor will have weekly/monthly contact with each participant randomized to the dietary and physical activity guidelines intervention group for the first year of the study. During this time, the counselor will inquire about each participant's overall health and how she is adapting to the dietary and physical activity guidelines intervention program.

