- a. What is the investigator's assessment of the overall risk level for subjects participating in this study? Minimal risk
- b. If children are involved, what is the investigator's assessment of the overall risk level for the children participating in this study? N/A
- c. Include an appropriate Data and Safety Monitoring Plan. Examples of DSMPs are available here <http://www.yale.edu/hrpp/forms-templates/biomedical.html> for
 - i. Minimal risk
 - ii. Greater than minimal
 - iii.

The principal investigator is responsible for monitoring the data, assuring protocol compliance, and conducting the safety reviews at the specified frequency [semi-annually]. During the review process the principal investigator will evaluate whether the study should continue unchanged, require modification/amendment, or close to enrollment.

The principal investigator, the Institutional Review Board (IRB) have the authority to stop or suspend the study or require modifications.

This protocol presents minimal risks to the subjects and Unanticipated Problems Involving Risks to Subjects or Others (UPIRSOs), including adverse events, are not anticipated. Adverse events are defined as injury possibly associated with participation in the physical activity component of the intervention. In the unlikely event that such events occur, Reportable Events (which are events that are serious or life-threatening and unanticipated (or anticipated but occurring with a greater frequency than expected) and possibly, probably, or definitely related) or Unanticipated Problems Involving Risks to Subjects or Others that may require a temporary or permanent interruption of study activities will be reported immediately (if possible), followed by a written report within 5 calendar days of the Principal Investigator becoming aware of the event to the IRB (using the appropriate forms from the website) and any appropriate funding and regulatory agencies. The investigator will apprise fellow investigators and study personnel of all UPIRSOs and adverse events that occur during the conduct of this research project via email as they are reviewed by the principal investigator.

d. For multi-site studies for which the Yale PI serves as the lead investigator: YES.

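### Adverse events are defined only as exercise-related injury, so diet-related harm and essentially any usual-care event fall outside adverse event reporting, and no between-arm safety comparison is prespecified

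*Combined protocol and SAP*

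**What the plan says.** The definition is "Adverse events are defined as injury possibly associated with participation in the physical activity component of the intervention". It stands in Section I, item 11, in both the minimal-risk plan (part c) and the multi-site plan (part d), and again in Section IV in the answer on safeguarding study data. No wider definition appears anywhere.

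The program is broader than exercise. In the description of the counseling sessions, "The nutrition counseling promotes a predominantly plant-based diet". A registered dietitian delivers 16 sessions over 12 months, beginning around the start of chemotherapy. Malnourished women are excluded on the PG-SGA, which the assessment schedule lists at screening only.

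On contact, Section I, item 9 (Risks) says "The nutritionist/counselor will have weekly/monthly contact with each participant randomized to the dietary and physical activity guidelines intervention group" for the first year, and that "the counselor will inquire about each participant's overall health and how she is adapting to the dietary and physical activity guidelines intervention program". No matching contact is described for usual care. On what usual care receives, the protocol says "we will also give women randomized to usual care a lifestyle intervention book and log book for breast cancer survivors", with access to online videos.

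Item 11 also has an expedited route: "Unanticipated Problems Involving Risks to Subjects or Others that may require a temporary or permanent interruption of study activities will be reported immediately". Item 12 (Statistical Considerations) sets out analyses of relative dose intensity, dose reduction, endocrine adherence and the secondary endpoints. It contains no safety analysis by arm.

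**The concern.** Two features of the definition matter. First, it covers one of the two components. The protocol treats nutritional status as important enough to exclude malnourished women. Its background links low lean mass to greater treatment toxicity, and enrollment is not restricted by BMI. Yet a nutritional harm could not be logged as an adverse event.

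Second, it builds relatedness to the program into what counts as an event. That removes the background rate in the control arm, which is what randomization is there to supply. Exercise-related injuries would be counted in one arm with nothing to set them against.

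The investigator's review of event frequency and severity and the annual summary to the ethics committee (item 9), and the risk/benefit judgment (item 11), all draw on events so defined. Any later statement that the program is safe during chemotherapy could not rest on adverse event rates.

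**Working it through.** The documents give no adverse event rate or safety sample size, so there is no figure to reproduce. The check sets the definition against the rest of the protocol.

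1. **Arm.** The definition requires participation in the intervention's physical activity component. The planned total is 172, so 172 / 2 = 86 per arm, as in the power section. Usual-care women receive a book, a log book and videos, but do not join that component. Their expected count is essentially zero by construction, so a difference in rates has no interpretation.

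2. **Component.** A harm from diet counseling is not an injury from physical activity, so it is not an adverse event. The same applies to the blood-draw risks listed in item 9.

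3. **Ascertainment.** Counselor questioning about health is described for the intervention arm only. Symptom questionnaires have no arm restriction, and every patient sees her oncologist at each chemotherapy session. The asymmetry therefore lies in counselor contact and does not extend to all health information.

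4. **What is collected outside the definition** (assessment schedule and Section I, items 1, 3 and 12):

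| Measure | When | Limits | Stated between-arm analysis |
|---|---|---|---|
| PRO-CTCAE | baseline, post-chemotherapy | stops after chemotherapy | none |
| Neuropathy (CIPN20), BCPT symptoms, pain | baseline, post-chemotherapy, 1, 2, 5 years | none by arm or site | none named as safety; the first two are described under quality of life, so may fall under Aim 2c |
| Lymphedema | 1, 2, 5 years | no baseline | none |
| Weight, DXA | baseline, post-chemotherapy, 1, 2 years | optional; Yale in-person only; suspended from mid-March 2020 | Aim 2b, change modelled by treatment |
| Dose reductions, delays, reasons | during chemotherapy | none by arm | primary endpoint family |
| PG-SGA | screening | not repeated | none |

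5. **Size of the coverage limits.** Chemotherapy is said to last 3 to 5 months and the intervention 12. PRO-CTCAE therefore leaves about 12 - 5 = 7 to 12 - 3 = 9 months of the program uncovered. The Yale target is 133 of 172, so measured weight and DXA could reach at most about 133 / 172 = 77% of planned women, before allowing for refusals and the pandemic suspension.

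**The case against.** A reader might infer that a safety comparison is impossible and that diet-related harm is not captured at all. The documents do not support either. Patient-reported toxicity, neuropathy, pain and lymphedema are scheduled for all women. Weight and lean mass are Aim 2b endpoints modelled by treatment with a baseline covariate. Relative dose intensity and dose reduction are tested between arms, and reasons for dose changes are summarized by group. Much of what one would worry about already has a randomized comparison or the data for one.

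Nor can one infer that such harms never reach the investigator. Part d of item 11 and Section IV have the investigator review study data as well as adverse events. Unanticipated problems are a wider class than adverse events and are not tied to exercise or to one arm. Dietitians also check food records against individual goals and adapt foods to keep intake adequate.

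Finally, safety is not a stated aim, and the study is assessed as minimal risk.

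All of this stands, and it narrows the point. It does not remove it. The unanticipated-problem route is for expedited reporting and would not tabulate ordinary nutritional or symptom harm by arm. The general review of study data promises no comparison by arm. None of the measures in the table is designated as safety data. The minimal-risk rating is the investigator's own assessment, and a definition that leaves out one component cannot test it.

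**Conclusion.** The point holds in limited form. Followed as written, the definition leaves diet-related harm and essentially all usual-care events outside adverse event reporting, so adverse event rates cannot be compared by arm. No between-arm safety comparison is prespecified, although suitable data are scheduled in both arms.

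This rests on two assumptions: that the definition is applied literally, and that receiving a book and videos does not count as taking part in the physical activity component. If a site took a looser view of the second, a few usual-care events might be logged, but inconsistently.

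The size in events cannot be estimated. What can be stated is structural: one of two components is uncovered, and one of two arms has a count near zero by design. The consequence is for safety oversight and for what can be said about safety. The primary efficacy analysis is unaffected.

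**What to change.** Reword the definition in all three places to cover untoward events in either arm and from either component, with relatedness judged as a separate step. Record events in both arms at the assessments already scheduled for all women: post-chemotherapy, 1 year and 2 years.

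Prespecify one by-arm safety table in item 12: PRO-CTCAE at post-chemotherapy adjusted for baseline, and lymphedema at 1 and 2 years. Cross-reference the planned weight and lean-mass comparisons as safety data, and include them in the periodic safety review.

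The cost is monitoring-plan wording, one table and somewhat more events to log. No new visit is needed, but asking about events in usual care is additional work. Three limits should be stated with the table:

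- PRO-CTCAE ends at post-chemotherapy although the intervention runs for a year.
- Weight and DXA are optional, Yale in-person only, and were suspended from mid-March 2020.
- Counselor contact over 16 sessions can still raise detection in the intervention arm, so events elicited by the counselor should be tabulated separately from those found at the common assessments.

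The same passages disagree on other matters and should be reconciled in the same edit. Safety review is every six months in item 9 and in item 11, part c, but quarterly in item 11, part d, and in Section IV. Written reporting is within 5 calendar days in part c, but within 48 hours in part d and in Section IV.
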